## 5. COPD MANAGEMENT STRATEGIES AND MEDICAL DEVICES

---

### 5.A DESCRIPTION OF COPD MANAGEMENT STRATEGIES AND OF MEDICAL DEVICES

The study will compare a Home-Based COPD Management Program (*Intervention group*) versus a usual patient education and follow-up (*Control group*). Patients of both study groups will be equipped with the *NOWOX* device to monitor oxygen therapy if they are on oxygen therapy at Selection or during their study participation.

#### 5.A.1 *Home-Based COPD Management Program*

The study Home-Based COPD Management Program consists in:

- A specific COPD educational program,
- A specific COPD prospective telephone follow-up.

##### 5.A.1.1. Study specific COPD educational program

The educational program used in this study is adapted from the validated program “Living well with COPD”. The original program was developed to be delivered by trained health professionals to patients with COPD and includes patient education materials (*handbooks, brochure and written action plan*) and supportive teaching materials for the trainers (*guides and flipchart*). Original materials were developed in two languages (*Canadian French and Canadian English*) and are available on the “[www.livingwellwithcopd.com](http://www.livingwellwithcopd.com)” website.

Adaptation of the original program for the needs of study was performed by a team composed of [name], the owner of the program, health professionals of the McGill University (*Montreal, Canada*) and health professionals specialised in respiratory diseases of the 4 study countries.

The education materials that will be used in the study (*Table 1*) were adapted from the originals for the purpose of this study to account for:

- The severity of the study disease. Content of the program has been adapted to the severity of the patients who will be enrolled as patients with GOLD III/IV COPD and especially those with chronic respiratory failure have different capabilities compared to a general COPD population for which the original education program was developed,
- The number, modalities and content of the patient educational sessions. Content of the training and related patient and trainers materials were adapted to the planned study individual/group/phone education sessions (*content and materials are summarised in Table 1*),
- The study countries. Education documentation for patients and trainers have been translated in the four (4) study languages and adapted for cultural differences from the Canadian French version of the original program.

**Table 1:** Content of the Study Specific COPD Educational Program

Session	Duration (min)	Topics	Living well with COPD materials for patients	Living well with COPD materials for health counsellors
Individual # 1	60-90	
 
- Knowledge assessment
 
- Disease knowledge: defining COPD, risk factors and symptoms; COPD medication, including oxygen therapy
 
- Behaviour change: compliance to medication
 
- Self-management skills: correct use of COPD medications
 
	
 
- Handbook “Understanding COPD and taking your medication”
 
- Handbook “Long term oxygen therapy”
 
- Brochure “Summary guide”
 
	
 
- Trainer guide “Understanding COPD and taking your medication”
 
- Flipchart
 

Individual # 2	60-90	
 
- Knowledge assessment
 
- Disease knowledge: dyspnoea; stress and anxiety factors
 
- Behaviour change: manage breathing and stress and save energy
 
- Self-management skills: techniques for breathing, coughing, managing stress and anxiety; energy conserving techniques
 
	
 
- Handbook “Breathing and stress management, and energy conservation”
 
- Brochure “Summary guide”
 
	
 
- Trainer guide “Breathing and stress management, and energy conservation”
 
- Flipchart
 

Individual # 3	60-90	
 
- Knowledge assessment
 
- Disease knowledge: evaluate chronic symptoms; identify and avoid triggers
 
- Behaviour change: prevent and manage symptoms aggravation
 
- Self-management skills: symptoms monitoring; avoidance of aggravating factors; respiratory self-assessment; managing symptoms worsening
 
	
 
- Handbook “Integrating an action plan into your life”
 
- Written action plan
 
	
 
- Trainer guide “Integrating an action plan into your life”
 
- Flipchart
 

Individual # 4	60-90	
 
- Knowledge assessment
 
- Disease knowledge: importance of nutrition, sleep and physical activity
 
- Behaviour change: smoking cessation; compliance to medication; maintain an active life; integrate healthy habits in everyday life
 
- Self-management skills: methods to increase physical and leisure activities, while adhering to oxygen therapy; keep healthy sleep and nutrition habits
 
	
 
- Handbook “Adopt and maintain a healthy lifestyle”
 
- Module “Long term oxygen therapy”
 
- Brochure “Summary guide”
 
	
 
- Trainer guide “Adopt and maintain a healthy lifestyle”
 
- Flipchart
 

Group	90-120	
 
- Needs assessment
 
- Behaviour change: maintenance of healthy habits and integration of self-management skills for life
 
- Self-management skills: brief review of all self-management techniques; focus on action plan: symptoms monitoring, respiratory self-assessment; managing symptoms worsening
 
	
 
- Handbook “Integrating an action plan into your life”
 
- Written action plan
 
	
 
- Trainer guide “Group session”
 
- Flipchart
 

Phone	30	
 
- Assessment of behaviour change: integrated behaviours, barriers to change and reasons (knowledge, beliefs, etc...)
 
- Self-efficacy reinforcement on various self-management skills
 
		
 
- Standardised educational phone interview
 

The program will be administered to the patient by health professionals (*nurses, physiotherapists, ...*), called for the study purpose “health counsellors”, especially trained to educate COPD patients and to the education program. Duration of each session, content and related materials are listed in Table 1.

#### 5.A.1.2. Study specific COPD prospective telephone follow-up

Patients will have to report their clinical status by telephone to a dedicated, full free, vocal server at least once a week (*and at most once a day*) and each day their clinical status is worse than usual. During the phone call, the patients will enter their study identification number and will answer a questionnaire in their native language by pressing numbers on their touch-tone phone. Patient’s answers will lead to an automatic scoring of their clinical status (*a sample of the script of the questionnaire and methodology to assess the clinical status score is provided in Appendix 2*).

Results of the scoring will determine the actions to be taken by the patient, the health counsellor and the investigator (*as detailed in Appendix 2*). In brief, in case of significant clinical status deterioration, the patient will perform at home a respiratory self-assessment (*measurements of FEV1, SpO2 on room air and also on oxygen for patients on oxygen therapy, pulse rate and temperature*); the health counsellor will provide support and reinforcement, and the investigator will call the patient to provide his/her medical decision.

#### **5.A.2 Usual COPD education and patient follow-up**

The usual COPD education and patient follow-up will be defined as the ones in force during the study in the investigational centres.

The current routine of each centre will be collected before study initiation, as well as any modifications afterwards.

#### **5.A.3 Oxygen sources**

Oxygen prescriptions to the study patients will follow the standard protocols of the investigational centres, and they will be at the investigator’s discretion throughout the study period.

#### **5.A.4 Medical devices**

##### 5.A.4.1. NOWOX

[figure not shown]
The medical device *NOWOX* (*Figure 2*) is small (*dimensions are 58 \* 28 \* 60 mm*), light (*total weight of 30 g*), wireless, and maintenance free. It is made of RADEL R and CE-marked.

**Figure 2:** *NOWOX* Device

The *NOWOX* is connected in line between the oxygen source and the patient nasal cannula as shown in Figure 3. The device is compatible with standard nasal cannulae and standard oxygen tubing.

**Figure 3:** *NOWOX* Connection Between the Nasal Cannula and the Oxygen Source

The *NOWOX* is compatible with the following types of oxygen sources:

- Oxygen concentrators,
- Oxygen cylinders (*gaseous oxygen*),
- Stationary and mobile oxygen tanks (*liquid oxygen*).

Of note, *NOWOX* is not to be connected to the oxygen source when the patient is on a CPAP device or a home ventilator.

The device makes measurements every five minutes and stores the summarised data every hour. A data record contains the following fields:

- A unique numeric index to identify the record,
- The GMT date and time of the record,
- The percentage of time during which oxygen flow was detected during the past hour (*in percentage of one hour*),
- The percentage of time of oxygen use during the past hour (*in percentage of one hour*), defined by detection of simultaneous oxygen flow and patient's breathing,
- The average respiration rate recorded during the past hour (*in breaths per minute*),
- The peak respiration rate recorded during the past hour (*in breaths per minute*).

The data stored by the *NOWOX* will be downloaded by the manufacturer when the device is returned by the patient to the investigational centre (*i.e., at the end of the patient's participation in the study, or in case the device has to be replaced for any reason*) using a Personal Computer equipped with a radio frequency communication port and the dedicated software (*NOWOX monitor v1.0*). The data will be identified only with the device serial number, and will be saved on a CD-Rom, which will be sent to LINCOLN, in charge of the study data management. Then, they will be transferred electronically into the trial database (*see section 7.A*).

Ten percent of the *NOWOX* devices will be equipped with a GSM gateway, allowing the automatic sending of the data to a sponsor central server. GSM-equipped *NOWOX* data will be downloaded by the manufacturer as previously described after the return of the device to the investigational centre. Data sent through the GSM gateway will only be used by the sponsor to check major dysfunctions throughout the study conduct. These data sent through the GSM gateway will be identified only with the device serial number. They will not be recorded in the study database and will not be associated with the patient selection or randomisation numbers.

More information are provided in the current versions of the *NOWOX* and *NOWOX* gateway user manuals, both available in the 4 study languages.

#### 5.A.4.2. Oximeter

The medical device Onyx® 9500 (*Nonin Medical*) is a self-contained digital fingertip pulse oximeter, incorporating the electronics and sensor in one unit. It measures instantaneous SpO2 and pulse rate. This product complies with current ISO references, current Medical Devices Directive and is CE marked. User manuals are available in the 4 study languages.

#### 5.A.4.3. Spirometer

The Vitalograph® asma-1 (*Vitalograph*) is a portable medical device measuring lung function (*FEV1* and *peak expiratory flow*). The device allows the setting of personal best or predicted (*reference*) values. It complies with current ISO references, current Medical Devices Directive, and is CE marked. User manuals are available in the 4 study languages.

#### 5.A.4.4. Thermometer

The electronic ear and forehead thermometer (*ref. 13673-56, Orgalys*) is a medical device measuring temperature instantly and accurately. Measuring range is 32.0°C - 42.9°C with an accuracy of ± 0.2°C from 36.0°C to 39.0°C. The device complies with the current Medical Devices Directive and is CE marked. User manuals are available in the 4 study languages.

## 5.B PACKAGING AND LABELLING OF THE MEDICAL DEVICES

### 5.B.1 *NOWOX*

The *NOWOX* devices will be supplied with the user manual in a box according to European regulations. The trial protocol number “ALMED-07-C4-008” will be stuck on each packaging and each device will have an individual serial number.

Each time a *NOWOX* device is assigned to a patient, the investigator will report the *NOWOX* serial number in the patient’s e-CRF as detailed in section 4.B.3.

### 5.B.2 *Oximeter, spirometer and thermometer*

The oximeter, spirometer and thermometer devices will be supplied with their user manuals, according to European regulations. The trial protocol number “ALMED-07-C4-008” will be stuck on each packaging and on each device.

## 5.C STORAGE, ACTIVATION, USE AND RETURN OF THE MEDICAL DEVICES

### 5.C.1 *NOWOX*

The *NOWOX* devices are shut down after manufacturing to preserve their battery. They can be stored for one year away from a heat source, without shortening their useful life. After a device has been activated, the battery life time is 2 years. In any case, if the battery runs out, the data stored by the *NOWOX* devices are saved and can be downloaded.

The *NOWOX* device has to be activated once prior to its use, before its connection to the nasal cannula and the oxygen source, by inserting a paperclip twice in the reset pinhole (*detailed procedure is described in the NOWOX user manual*). A blinking optical control (*several blue flashings*) indicates that the device has gone through a self-test and is functional. The device is then connected to the patient nasal cannula and to the oxygen source.

The recommendations for use of the *NOWOX* and the specific Material Safety Data Sheet are detailed in the *NOWOX* user manual. A risk analysis has been performed by the sponsor and the manufacturer of the *NOWOX* in accordance with the standard ISO 14971 (*application of risk management to medical devices*).

Used and unused devices and their related materials (*NOWOX devices, NOWOX GSM gateways, and documentation*) will be returned to the sponsor at the end of the trial.

### 5.C.2 *Oximeter, spirometer and thermometer*

Used and unused devices and their related materials and documentations will be returned to the sponsor at the end of the trial.

## 5.D CONCOMITANT TREATMENTS

All concomitant treatments administered to the patient (*including vaccines, oxygen therapy, home ventilation and CPAP*) will be recorded by the investigators in the e-CRF, with the following information:

- **For the pharmaceutical therapies:** treatment names and dosage, route of administration, dose per administration and posology, start and end dates or ongoing medication, and the reason for their prescription,
- **For the vaccines:** names and date of administration,
- **For oxygen therapy:** start and, if applicable, end dates, daily prescribed hours of use, prescribed flow rates (*at rest, during exercise and during sleep*), type of oxygen source(s) including the name of the device(s) used,
- **For home ventilation and CPAP:** start and end dates, if applicable.

### **5.D.1**     *Allowed medications*

All COPD and non-COPD medications which are deemed necessary by the investigator for the patient's welfare may be administered at any time at the investigator's discretion. They will be recorded accordingly in the e-CRF.

### **5.D.2**     *Not permitted medications*

Long term oral corticosteroids therapy is not permitted at Selection. Long term use is defined as continuous use of > 10 mg of prednisone or equivalent per day for more than 6 weeks. Successive courses of oral corticosteroids separated by a period of less than 7 days will be considered as continuous use.

However, if during the study *Follow-Up Period*, a patient requires such a therapy, he/she will not be withdrawn from the trial but the corresponding data must be recorded by the investigator in the e-CRF.

The patients will not be allowed to participate to any other interventional study during their participation to this trial.

## 6. STUDY EVALUATIONS

---

### 6.A EFFICACY EVALUATIONS

#### 6.A.1 *Primary efficacy criterion*

The primary efficacy criterion is the **number of unscheduled hospital days, whatever the reason, during the *Follow-Up Period*** for each randomised patient.

Hospitalisations are defined as stays in the following facilities:

- Emergency room, if duration of stay is > 24 hours,
- Intensive care unit, intermediate care unit, surgical or medical wards,
- Nursing facilities following an acute hospital stay.

Scheduled inpatient rehabilitation will not be considered as hospitalisations.

The number of unscheduled hospital days will be calculated for each randomised patient based on the following information recorded by the investigators in the e-CRF for each hospitalisation separately during the *Follow-Up Period*:

- Reason for admission,
- Type of facility,
- Dates of admission and discharge for each facility.

These data will be normalised by total number of days that the patient will have participated in the *Follow-Up Period* to yield the duration of hospitalisations per year, as detailed in section 7.B.3.5.

Each hospitalisation will also be reported as a Serious Adverse Event as defined in section 8.A.

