#### 6.A.2.3. Use of health care services due to COPD and to all causes

**The investigators** will record the following information about use of health care services during the *Follow-Up Period*:

- For each medical or paramedical consultation: date, type of visit (*home versus out-patient visit*), category of health care provider consulted (*specialist physician, primary care physician, nurse, respiratory therapist, ...*) and the reason for consulting,
- Home hospitalisation: start and end dates.

**The health counsellors** will record the following information about use of health care services during the *Follow-Up Period* (*for the Intervention group only*):

- For each unscheduled phone call (*on patient's request or because of the symptom scoring*): date, duration of the phone call and the reason for calling.

If any of the use of health care services recorded are the results of an AE or SAE, then the appropriate e-CRF should also be completed by the investigator.

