## **6.C MEDICO-ECONOMIC EVALUATIONS**

### **6.C.1 Costs estimation**

Overall costs will be estimated for each randomised patient from the perspective of the health care payer (*i.e.*, the National Health System in force in the country, with the latest version of the corresponding national tariffs system and reimbursement schedule available at the end of the study). The unit will be the patient. Only health care direct costs will be considered, neither the costs to the family nor the costs to the society will be estimated.

Overall resources used for the patient's medical management (*collected in volume, i.e., by type and/or unit of time, before being priced according to the national tariffs system in force*) will be recorded prospectively alongside the study by the study personnel, as the data used to estimate the overall costs from the perspective of the health care payer for each randomised patient have four (4) components which are part of the clinical parameters recorded, including:

- For each unscheduled hospitalisation (*including home hospitalisations*): the dates of admission and discharge, the type of facility, the primary and secondary diagnoses (*as mentioned in section 6.A.1*), as well as the additional expensive medical procedures and acts performed during hospitalisation, if relevant (*including laboratory and other diagnosis examinations*), and the specific expensive treatments administered or technical devices and equipments used during hospitalisation, whenever possible,
- For each health care consultation: the date, the location, the category of health care provider consulted and the reason for consulting (*as detailed in section 6.A.2.3*),
- For the patients in the Intervention group and for each unscheduled phone call to the health counsellor (*on patient's request or because of symptom scoring*): the date, the reason for calling, as well as the duration of the phone call and associated procedures set up by the health counsellor, and duration of the investigator actions in case of confirmed alarm status (*as mentioned in section 6.A.2.3*),
- For the patients in the Intervention group and for each scheduled education session: the date and duration of the education session performed, its type and location.

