### **6.C.2 Cost-effectiveness**

The cost-effectiveness evaluation performed will relate the estimated difference in costs between both COPD management programs in the perspective of the health care payer to a difference in medical outcome over the 12-month *Follow-Up Period*. The medical outcomes which will be taken into account in this evaluation will be:

- the number of unscheduled hospital days whatever the reason for hospitalisation (*i.e., the primary efficacy criterion defined in section 6.A.1*),
- the number of deaths.

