## **COST-EFFECTIVENESS**

If this main medico-economic evaluation reveals a statistically significant study group difference, at level  $\alpha = 0.05$ , in a given country, in a second step, the overall costs per patient, from the perspective of the health care payer will be related to the primary efficacy criterion, by estimating a cost per unscheduled hospital day avoided whatever its reason in each study group, separately.

Average overall costs and benefits will be estimated with Kaplan-Meier's sample averages and bootstrap replications, before calculating the 95.0% confidence intervals of Incremental Cost-Effectiveness Ratios (*ICERs, i.e., the overall net costs (defined as the difference in overall costs on the Home-Based Disease Management Program – those on the usual program) divided by the corresponding net benefits (i.e., the difference in both numbers of unscheduled hospital days whatever their reason)*).

If performed, this cost-effectiveness evaluation will be repeated, by relating the overall costs per patient, from the perspective of the health care payer, to the number of deaths, in each study group separately, by replacing the previous denominator of the calculated ICERs by the difference in the numbers of deaths in both study groups.

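### Home hospitalisation lies outside the primary hospital-day count but inside the cost definition of unscheduled hospitalisation, and no planned analysis adds home days to ward days

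*Protocol*

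**What the plan says.** The primary criterion in section 6.A.1 is the "number of unscheduled hospital days, whatever the reason, during the" Follow-Up Period. The section then gives the definition: "Hospitalisations are defined as stays in the following facilities". The list covers emergency-room stays over 24 hours, intensive and intermediate care, surgical and medical wards, and nursing facilities after an acute stay. One exclusion is spelled out: "Scheduled inpatient rehabilitation will not be considered as hospitalisations". Home hospitalisation is neither listed nor expressly excluded.

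It appears in two other places. Section 6.A.2.3, a secondary criterion on health care use, has investigators record "Home hospitalisation: start and end dates", with no restriction to one arm. Section 6.C.1 requires cost data for each unscheduled hospitalisation, "including home hospitalisations", and refers back to 6.A.1 in the same item.

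The cost-effectiveness outcome in 6.C.2 is "the number of unscheduled hospital days whatever the reason for hospitalisation", tied expressly to 6.A.1. The denominator of the incremental cost-effectiveness ratio (ICER) in 7.B.3.6 is "the difference in both numbers of unscheduled hospital days whatever their reason".

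**The concern.** One episode of acute care at home is an unscheduled hospitalisation in the costs and nothing in the primary count. The list in 6.A.1 cannot be read simply as hospital walls only, because it admits nursing facilities after an acute stay.

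The omission matters because the trial is open (4.B.2), the programme is home-based partly because patients wish to stay at home and to save cost (1.B), and 6.D accepts that the decision to admit varies with the physician, the centre and social circumstances. If acute care moved from ward to home more in one arm than in the other, the primary criterion would differ between arms by that amount even with equal total acute-care days. A reader of the result could not tell fewer acute-care days from the same days spent elsewhere.

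Section 6.A.2.2 has a related gap. Severe exacerbations require hospitalisation or lead to death; moderate ones do not require hospitalisation. An exacerbation managed by home hospitalisation is not assigned to either.

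**Working it through.** **1. The definitions side by side**

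| Protocol section | Use | Home hospitalisation |
|---|---|---|
| 6.A.1 | primary count | not listed, so 0 days |
| 6.A.2.2 | severe or moderate exacerbation | not addressed |
| 6.A.2.3, 7.B.3.5 | health care use, each category compared by group | dates recorded, analysed separately |
| 6.C.1 | costs | counted as unscheduled hospitalisation |
| 6.C.2, 7.B.3.6 | days avoided | follows 6.A.1, so 0 days |
| 6.D, 7.B.3.5 | repeat on committee-confirmed stays | not stated to be added |

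No section reconciles these entries. The per-protocol repeat, the analysis of variance and the committee-based repeat all use facility days.

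**2. The plan's own figure (7.B.2)**

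Inputs: difference 10 days, SD 25, two-sided alpha 0.05, power 0.90, 6.25% without usable data.

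- p = Φ(10/(25√2)) = 0.6114
- Noether: n = (1.960 + 1.282)² / (6 × (0.6114 − 0.5)²) = 141.2, so 142 per group against 143 stated
- Dropout: 143/(1 − 0.0625) = 152.5, so 153 per group and 306 in total, as stated

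The sample size reproduces closely and is not in dispute.

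**3. What a move does to the criterion**

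Let T be mean acute-care days per patient-year (ward plus home) and H the home part. The primary count is W = T − H, so

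W(Control) − W(Intervention) = [T(Control) − T(Intervention)] + [H(Intervention) − H(Control)].

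The first bracket is a change in acute-care days. The second is place of care and can have either sign. If T is equal in both arms and s days move home in the Intervention arm only, the criterion shows a reduction of exactly s.

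**4. Illustration on the plan's scale**

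With n = 143 per group, SD 25 and a normal shift, the chance of a significant result favouring the programme is Φ(√(6n) × (p_s − 0.5) − 1.960), where p_s = Φ(s/(25√2)).

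| s (days) | chance |
|---|---|
| 0 | 2.5% |
| 2 | 10% |
| 5 | 38% |
| 10 | 90% |

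**5. Sensitivity to the assumed distribution**

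The protocol gives no mean number of days, no proportion of patients with zero days and no rate of home hospitalisation, so every input below beyond the SD of 25 and the 143 per group is assumed.

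Model A: 40% of patients with zero days, SD 25, equal total days, a fraction of Intervention ward days moved home; two-sided rejection, 2,000 runs.

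| fraction moved | mean 15 days | mean 20 days |
|---|---|---|
| 0 | 5.7% | 5.6% |
| 10% | 5.5% | 6.3% |
| 25% | 11% | 22% |
| 50% | 50% | 74% |

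Model B: negative binomial admissions, mean 1.8 per year, mean stay 11 days (mean 20, SD 27 days), whole Intervention episodes moved and none in Control; rejection favouring the programme, 1,500 runs. Moving 10%, 20% or 30% gives differences of about 2, 4 or 6 days and rejection in 9%, 24% or 50% of trials, against 3% with none moved.

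The models agree on direction but not on size. At 10% moved, Model A shows almost no effect.

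**The case against.** The strongest reply is that hospital days are the stated target. Section 1.C hypothesises fewer admissions or less time in hospital, and 7.B.3.5 tests equality of the distributions of hospitalisation duration. If care moves home, hospital days do fall and rejecting that null is correct. This stands. It is why the primary criterion should be kept and why the rates above are not false-positive rates for the protocol's hypothesis.

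Second, home hospitalisation is recorded in both arms and compared by group as health care use, so a move could be seen. This stands in part: the comparison is exploratory and never combines home and ward days within a patient.

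Third, a sensitivity analysis can be left to the statistical analysis plan, which is not shown. That is fair for the analysis, but the two definitions are in the protocol and need reconciling there.

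Two stronger readings may tempt a reader. One is that Appendix 2 gives Intervention patients alone a route to home hospitalisation. It does not: the decisions listed after an alarm are no action, therapeutic adjustment, a physician visit, or emergency attendance or hospitalisation. The programme is education and telephone follow-up, and alarms could equally raise admissions. The other is that the ICER is invalid because its numerator holds home-stay costs and its denominator omits those days. A payer's cost numerator properly holds all resources, including consultations and education sessions that have no counterpart in the day count. Keeping home-stay costs there charges any substitution to the programme.

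**Conclusion.** The definitional conflict is plain on the text: 6.A.1 leaves home hospitalisation out and 6.C.1 counts it as an unscheduled hospitalisation. It follows by algebra that a differential move of s days shifts the primary criterion by s days, with each home day assumed to replace one ward day. Whether such a move would occur, in which arm and how large, cannot be determined from the protocol.

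A reader might infer that a significant primary result would probably be relabelled care. The documents do not support that: the fractions moved, the admission rate and the length of stay are all assumed, and zero home hospitalisation in Control is the extreme case. What is supported is narrower. As planned, the trial cannot fully separate fewer acute-care days from acute care given at home, although data to address this are already collected. This is a worthwhile, inexpensive improvement and not a flaw that invalidates the primary analysis.

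**What to change.** Keep the primary criterion and the sample size.

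- **6.A.1 and 6.C.1:** state in 6.A.1 that home-hospitalisation days are not counted, and reword 6.C.1 so that home hospitalisation is a separately named cost item and not a kind of unscheduled hospitalisation.
- **7.B.3.5:** pre-specify one sensitivity analysis repeating the Wilcoxon test, with the same yearly normalisation, on facility days plus home-hospitalisation days, using the dates collected under 6.A.2.3 and counting a transfer day once. Show it beside the primary result.
- **6.A.2.2:** report exacerbations managed by home hospitalisation as a separate category.
- **7.B.3.6:** keep home-hospitalisation costs in the ICER numerator. Optionally add a ratio per combined hospital-plus-home day avoided.

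The cost is a few lines of wording and one extra analysis on data already collected. The drawback is that the added analysis may be less favourable than the primary.
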